### 7.3 Vital Signs

Vital sign measurements will be summarized descriptively by target visit using the visit windows defined in [Appendix A](#) and the last available on-treatment visit; baseline will be the last non-missing value prior to the first dose of study drug. The baseline data may come from the prior study, if not repeated in 020. Vital signs include seated blood pressure and pulse, temperature, respiratory rate, and body weight. Change from baseline will also be calculated and summarized. If a subject has multiple values within a visit window, the “worst” value as defined in [Appendix D](#) will be used for that visit window summary.

Potentially clinically significant vital sign changes are defined for selected parameters in [Appendix C](#). When there are thresholds provided for low and high values, they will be handled separately. Summaries will include the number and percent of subjects with treatment-emergent PCS values, restricted to those subjects in whom the values represent a post-baseline worsening (PCST). A PCST is defined as any PCS event that happened at any post-baseline visit and has a value more out of range than the value for a particular parameter at baseline (see [Appendix D](#) for directionality of worsening).

Listings of vital sign measurements including height at Screening will be presented. Listings will flag results that meet criteria as being PCS (whether or not a treatment emergent worsening).

Separate listings for each vital sign parameter will include only subjects with study-emergent PCS values and, for these subjects, all corresponding vital sign results will be provided.

#### **7.4 Physical and Neurological Examinations and Serotonin Syndrome (Toxicity)**

Targeted examinations were optional prior to protocol version 3.0. With version 3.0 or higher, they are to be performed at every visit (or upon early termination), including the 4-week post-treatment follow-up visit if applicable.

The targeted examinations will be focused on, but not limited to, evaluating subjects for potential serotonin toxicity and also as clinically indicated. At a minimum, they are to include assessments for serotonin toxicity, evaluation of deep tendon reflexes, clonus, and muscle rigidity; size and reactivity of pupils; dryness of oral mucosa; intensity of bowel sounds; skin color; and presence or absence of diaphoresis.

Summaries will present the number and percentage of subjects with normal and abnormal observations by body system/parameter evaluated. By-subject listings will detail any abnormalities.

Ratings for signs and symptoms of serotonin syndrome (toxicity), inclusive of the MMSE, were introduced in protocol version 3.0 and will be performed at each visit. A by-subject listing of all responses will be prepared. A separate listing will be provided for the Mini-Mental State Examination (MMSE) scores.

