9.2 Sample Size Calculations

Not applicable to this open-label extension study.

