9.3.2 General Considerations

Results will be summarized descriptively; no inferential statistics are planned. Tabulations will be on the basis of all subjects pooled and also with subjects categorized separately by diagnosis and also by study of original participation. Data from the prior study will be mapped into the open-label database.

For purposes of calculations of change from baseline, Baseline (Visit 1) for the open-label study will be used. Depending on the parameter, the data may have been acquired during the double-blind study of prior participation.

For purposes of data tabulations, target visit windows will be assigned in the SAP.

Listings of by-subject data will be organized by subject number.

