9.6.4 Electrocardiogram

ECG results will be provided by the central ECG reader. Tabular summaries and analyses are to be based on the central ECG data. Machine-read ECG results and interpretations are to be recorded in the eCRF and included in a separate listing; this also applies to any subsequent local interpretations if used to make dosing or patient management decisions.

ECG interval data will be summarized based on the average of the triplicate measures. All other study visit ECG data (interpretations or means of triplicate measurements if

performed for clinical reasons) will be summarized separately. ECG interval and ventricular rate data will be summarized using descriptive statistics for both the original values and the change from Baseline. Windows for each target visit will be used (additional details provided in the SAP). Parameters to be analyzed include heart rate (HR) and PR, QRS, QT, and corrected QT (using Fridericia's and Bazett's corrections), and RR intervals. Counts and percent of subjects in each result category will be tabulated. Overall interpretations of abnormality(ies) will also be tabulated, with subjects categorized by whether or not they have treatment-emergent abnormalities.

Subjects are also to be categorized and enumerated on the basis of QTc interval and change from Baseline as follows:

- QTcB/F outliers (in categories of > 450 to ≤ 480 , > 480 to ≤ 500 , > 500 msec)
- Change in QTcB/F outliers (in categories of > 30 to ≤ 60 , > 60 to < 90 , ≥ 90 msec)

All HR, interval data, and interpretations will be listed. Any new finding after Baseline will be categorized into diagnostic groups: rhythm, conduction, hypertrophy, arrhythmia, ischemia, infarction, other.

9.6.5 *Physical and Neurological Examinations and Serotonin Syndrome (Toxicity)*

Physical and neurological examination results obtained at Baseline (Visit 1) will be summarized by body system. Evaluation at subsequent visits will be summarized in a treatment-emergent fashion. Summaries will present the number and percentage of subjects with normal and abnormal observations by body system/parameter evaluated. By-subject listings will detail the abnormality(ies). Ratings for signs and symptoms of serotonin syndrome (toxicity) will also be summarized. For each target visit, the number of subjects for whom "yes" is answered for any of the signs and/or symptoms will be tabulated. A by-subject listing of results will also be prepared.

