#### 4.1 Conventions

The precision of original measurements will be maintained in summaries, when possible. Means, medians and standard deviations will be presented with an increased level of precision; means and medians will be presented to one more decimal place than the raw data, and the standard deviations will be presented to two more decimal places than the raw data.

---

 Mapped data consists of medical history, concomitant medication, and AE data obtained during the prior studies and imported into the 020 database (for handling of these data see Sections 5.5, 5.6, and 7.1, respectively).

Unless otherwise specified, summaries of continuous variables that have some values recorded using approximate values (e.g., < or >) will use imputed values. The approximate values will be imputed using the closest exact value for that measurement. For tables where rounding is required, rounding will be done to the nearest round-off unit. For example, if the round-off unit is the ones place (i.e., integers), values  $\geq XX.5$  will be rounded up to  $XX+1$  while values  $< XX.5$  will be rounded down to  $XX$ .

For percentages, unless they are calculated to be exactly 0% or 100%, values of very small or very large percentages will be reported as  $<0.1\%$  and  $>99.9\%$ .

For by-visit tables, percentages will be based on available data and denominators will generally exclude subjects with missing values. For frequency counts of categorical variables, categories whose counts are zero will be displayed for the sake of completeness. For example, if none of the subjects discontinue due to “lost to follow-up”, this reason will be included in the table with a count of 0.

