**Table 14.3.4.4.1**  
**Serotonin Toxicity (Syndrome) Assessment by Visit**  
**Safety Population**

	Time point	AD (N= )	bvFTD (N= )	All Subjects (N= )
Sign or Symptom of Serotonin Toxicity (Syndrome) Exhibited 	Baseline	(n= ) n (%)	(n= ) n (%)	(n= ) n (%)
	Week 2	(n= ) n (%)	(n= ) n (%)	(n= ) n (%)
	...			

Note: Baseline is defined as the last non-missing value prior to first dose of study drug.

 Subjects are counted if they answered “yes” to any of the signs or symptoms on the Serotonin Toxicity (Syndrome) Assessment form.

path\t\_program.sas date time

*Programming note: Table will include all target visits and Last Available On-Treatment Value. Please see Appendix A for target visits and visit windows.*

*Programming Note: Repeat table for Table 14.3.4.4.2 Serotonin Toxicity (Syndrome) Assessment by Visit – Non-AChEI/Memantine Users (Safety Population)*

**Table 14.3.4.5.1  
Central ECG Data by Visit  
Safety Population**

ECG Parameter	Time Point	AD (N= )	bvFTD (N= )	All Subjects (N= )
Ventricular Rate (bpm)	Baseline 			
	N	n	n	n
	Mean (SD)	xx.x (xx.xx)	xx.x (xx.xx)	xx.x (xx.xx)
	Median	xx.x	xx.x	xx.x
	Min, Max	xx, xx	xx, xx	xx, xx
	Week 26			
	N	n	n	n
	Mean (SD)	xx.x (xx.xx)	xx.x (xx.xx)	xx.x (xx.xx)
	Median	xx.x	xx.x	xx.x
	Min, Max	xx, xx	xx, xx	xx, xx
	Change from Baseline to Week 26			
	N	n	n	n
	Mean (SD)	xx.x (xx.xx)	xx.x (xx.xx)	xx.x (xx.xx)
	Median	xx.x	xx.x	xx.x
	Min, Max	xx, xx	xx, xx	xx, xx
...				
PR Interval (msec)				
...				

 Baseline is defined as the mean of the last non-missing triplicate values prior to first dose of study drug.  
Note: The summaries are based on the measurements from central read (BIOCLINICA).

path\t\_program.sas date time

*Programming note: table will include all target visits and Last Available On-Treatment Value and the following ECG parameters: Ventricular Rate (beats/min), PR Interval (msec), QRS Duration (msec), QTcB Interval (msec), QTcF Interval (msec). See Appendix A for visit windows.*

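### SAP 7.4 omits the treatment-emergent summary of physical and neurological findings that protocol 9.6.5 requires, so the planned tables cannot show how many subjects developed a new finding

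*SAP*

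**What the plan says.** Protocol 9.6.5 gives three instructions for examinations:

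- Baseline: "Physical and neurological examination results obtained at Baseline (Visit 1) will be summarized by body system".
- Later visits: "Evaluation at subsequent visits will be summarized in a treatment-emergent fashion".
- Counts and percentages of normal and abnormal observations by body system or parameter.

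SAP 7.4 carries over only the third: "Summaries will present the number and percentage of subjects with normal and abnormal observations by body system/parameter evaluated". The shells for Tables 14.3.4.2 (physical) and 14.3.4.3 (neurological) print Normal, Abnormal NCS and Abnormal CS at Baseline and at each target visit. Neither has an emergent category or a cross-tabulation against Baseline. SAP section 9 names no change from the protocol and defers any to the study report.

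Three other provisions bear on how these tables read:

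- SAP 4.1, for by-visit tables: "percentages will be based on available data and denominators will generally exclude subjects with missing values".
- SAP 7.4: "Targeted examinations were optional prior to protocol version 3.0". From version 3.0 they are done at every visit.
- SAP 4.4: scheduled, unscheduled and early termination visits are assigned to the same analysis windows.

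**The concern.** Long-term safety is a primary objective, and the study has no control group. The within-subject comparison with Baseline is the one contrast that the protocol specifies for examination findings, and the planned tables do not make it.

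The omission is also out of line with the rest of the SAP. Section 1 says that safety reporting will be confined to study-emergent information. Sections 7.2, 7.3 and 7.5 keep an emergent or worsening rule for laboratory tests, vital signs and ECG, and ECG interpretation has a shift table (14.3.4.5.2). Only the examinations have none. A reader of the study report would see the percentage abnormal at each visit and could not tell long-standing findings from new ones.

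**Working it through.** The documents state no figure on this point. The protocol says in 9.3.2: "Results will be summarized descriptively; no inferential statistics are planned". There is nothing to reproduce, so the check compares the texts and then asks what the planned tables can determine. All rates below are assumptions.

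**1. Texts side by side.** The Baseline row in each shell meets the protocol's first instruction, and the per-visit counts meet the third. Nothing in SAP 7.4 or the shells meets the second.

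**2. What two per-visit percentages determine.** Let b be the proportion abnormal at Baseline, w the proportion abnormal at a visit, and p the proportion abnormal at both, in the same subjects. The newly abnormal proportion is n = w − p. Since p lies between max(0, b + w − 1) and min(b, w), n lies between max(0, w − b) and min(w, 1 − b).

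- b = 10%, w = 15%: n is between 5% and 15%.
- b = 30%, w = 35%: n is between 5% and 35%.
- b = 50%, w = 55%: n is between 5% and 50%.
- b = w = 30%: n is between 0% and 30%.

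The tables give b and w but not p, so they do not identify n.

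**3. Denominators.** The bounds in step 2 assume the same subjects at both times. Under SAP 4.1 the Baseline row and a visit row may describe different subjects, and then even these bounds are not assured. The laboratory tables deal with this through a by-visit Baseline row (Tables 14.3.3.1.1.1 and 14.3.3.2.1.1); the examination tables have no such row.

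**4. Optional and routine examinations together.** The version 3.0 change summary in protocol Appendix B says that earlier examinations were done as needed, after an adverse event or a change in the subject's condition. It is used here only to show how the early data arose. If a share s of the examinations in a window is on-demand, the pooled abnormal rate is (1 − s) × routine rate + s × on-demand rate. With assumed rates of 20% (routine) and 60% (on-demand):

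- s = 0%: 20%
- s = 10%: 0.9 × 20% + 0.1 × 60% = 24%
- s = 25%: 0.75 × 20% + 0.25 × 60% = 30%
- s = 50%: 0.5 × 20% + 0.5 × 60% = 40%

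The SAP does not say in words that it pools the two kinds. It also provides nothing to separate them.

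**The case against.** The case on the other side has weight. Each shell prints a Baseline row and grades findings NCS or CS. Listings 16.2.9.4 and 16.2.9.5 show each subject visit by visit. Protocol 7.1 requires a clinically significant abnormality to be recorded as an adverse event, so new ones should reach the study-emergent adverse event tables. Protocol section 9 allows changes of analysis to be documented in the final report. The protocol also asked for no split by protocol version.

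Much of this stands, but it does not replace the missing summary. Findings graded not clinically significant need not become adverse events. Tracing new findings by hand through listings, in a study that may enrol about 1050 to 1400 subjects, is not the summary that the protocol promised. A later note in the study report would disclose the departure without supplying the result.

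A reader might also infer that the serotonin table, 14.3.4.4.1, departs from the protocol in the same way, because it counts anyone answering yes "to any of the signs or symptoms on the Serotonin Toxicity (Syndrome) Assessment form" whatever was recorded at Baseline. The documents do not support that. Protocol 9.6.5 itself specifies the any-yes count at each target visit. SAP 7.4 says that the ratings began with version 3.0, so there are no earlier optional ratings to pool. Suspected serotonin toxicity is recorded as an adverse event of special interest and has its own study-emergent table (14.3.2.14.2.1).

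**Conclusion.** The point holds for the physical and neurological examination tables. A summary required by protocol 9.6.5 is missing from SAP 7.4 and both shells without being declared, and the number of subjects with a new finding cannot be recovered from the tables. The text comparison rests on no assumption. The size does: the documents give no abnormality rates and no share of on-demand examinations, so the ranges above only illustrate how wide the uncertainty can be. The change should be made, though adverse events and listings give partial cover meanwhile.

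Two stronger readings are tempting:

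- **That signs of dementia cannot be told from effects of LMTM because of this omission.** The adverse event tables and listings still carry emergent information. Nor would restoring the summary settle attribution: without a control group, a new sign from disease progression is also emergent. The 020 Baseline is not LMTM-naive for subjects previously treated with LMTM, and under protocol 6.2.1 bvFTD subjects may enrol on the day of their last dose in TRx-237-007.
- **That many subjects enrolled before version 3.0 lack a Baseline examination.** No document gives that count. SAP 4.2 allows Baseline data from the prior study, while the footnote to SAP 4.1 does not list examinations among the mapped data. Some may be missing; how many is unknown.

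**What to change.** In SAP 7.4 and the shells for Tables 14.3.4.2 and 14.3.4.3:

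1. Add Baseline-by-visit shift rows in the layout of Table 14.3.4.5.2.
2. Add a row for subjects normal at Baseline and abnormal after it. For this row and the shift rows, use subjects assessed at both times as the denominator.
3. Show optional examinations done before version 3.0 separately from routine ones under version 3.0 or later. Keep the earlier ones in the tables; removing them would lose safety information.
4. State which result counts when several examinations fall in one window, since Appendix D has no rule for examination findings.

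As an optional improvement, add to Table 14.3.4.4.1 a row for subjects with a serotonin sign not recorded at Baseline, beside the any-yes count that the protocol specifies.

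The cost is SAP text and two shells, or three with the optional row; no new data are collected. The downside is smaller denominators where the Baseline examination or rating is missing, so the number excluded for that reason should be printed.

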#### **7.5 Electrocardiography**

A 12-lead ECG (triplicate recording) was introduced in protocol version 3.0. Measurements are taken approximately every 6 months thereafter (or upon early termination), including the 4-week post-treatment follow-up visit if applicable. Recordings will be evaluated by a centralized ECG reading facility. Interval data (including QT and corrected QT intervals), ventricular rate, and overall interpretation are to be reported for every ECG. The interval data and ventricular rate are to be noted in the CRF as averages of the three readings (with the exception of values that are not evaluable and reported as zero, in which case the average will exclude this zero value and note in the CRF the average of values > 0).

ECG interval and ventricular rate data will be summarized using descriptive statistics. Windows for each target visit will be used ([Appendix A](#)). Parameters to be analyzed include heart rate (HR) and PR, QRS, QT, and corrected QT (using Fridericia's and Bazett's corrections), and RR intervals. Counts and percent of subjects in each result

category will be tabulated. Overall interpretations of abnormalities will also be tabulated, with subjects categorized by whether or not they have study-emergent abnormalities.

Subjects are also to be categorized and enumerated on the basis of QTcB/F interval as follows:

- Absolute measurements (in categories of  $> 450$  to  $\leq 480$ ,  $> 480$  to  $\leq 500$ ,  $> 500$  msec)
- Change from first 020 measurement (in categories of  $> 30$  to  $\leq 60$ ,  $> 60$  to  $< 90$ ,  $\geq 90$  msec)

All HR, interval data, and interpretations will be listed. Any local ECG results (optional prior to version 3.0 of the protocol) will be listed separately.

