## **4. GENERAL ANALYSIS CONSIDERATIONS**

The Safety population will include all subjects who take at least one dose of study drug. All analyses described in this SAP will be based on the Safety Population. All subjects entering the study, even if not known to have taken a dose, will be accounted for in a listing.

The statistical analyses will be reported using summary tables, figures, and data listings. Continuous variables will be summarized with means, standard deviations, medians, minimums, and maximums. Categorical variables will be summarized by counts and by percentage of subjects in corresponding categories.

For purposes of calculations of change from baseline, Baseline (Visit 1) for the open-label study will be used. Depending on the parameter, the data may have been acquired during the double-blind study of prior participation.

Summary tables will present results by diagnosis (AD or bvFTD) and an “All Subjects” column.

Individual subject data obtained from the CRFs (including mapped data), central clinical laboratory (local laboratory results are entered on the CRFs), and any derived data will be presented by subject in data listings. Listings will include relative study day, where negative values will indicate visits prior to first dose of study drug in 020, and any data collected after discontinuation of study drug will be flagged as follow-up. All data captured on the CRF, including specific descriptions of ‘other’ and comments fields, will be included on the listings. Listings will be sorted by subject number.

All analyses and tabulations will be performed using SAS® Version 9.4 or higher. Tables, listings, and figures will be presented in RTF format. Upon completion, all SAS® programs will be validated by an independent programmer. In addition, all program output will undergo a senior level statistical review. The validation process will be used to confirm that statistically valid methods have been implemented and that all data manipulations and calculations are accurate. Checks will be made to ensure accuracy, consistency with this plan, consistency within tables, and consistency between tables and corresponding data listings. Upon completion of validation and quality review procedures, all documentation will be collected and filed by the project statistician or designee.

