## 4.2 Standard Calculations

Variables requiring calculation will be derived using the following formulas:

- **Baseline** - A baseline value, unless specified otherwise, is the last non-missing value recorded prior to the first dose of study drug in 020. If an assessment has the same date as the date of first dose of study drug in 020, the assessment will be counted as baseline (depending on the parameter, the data may have been acquired during the double-blind study of prior participation).
- **Study day** – For a given date (*date*), study day is calculated as days since the date of first dose of study drug in the open-label extension (*firstdose*):  
Study day =  $date - firstdose + 1$ , where  $date \geq firstdose$   
Study day =  $date - firstdose$ , where  $date < firstdose$
- **Days** – Durations, expressed in days, between one date (*date1*) and another later date (*date2*) are calculated using the following formula: duration in days =  $(date2 - date1 + 1)$ .
- **Weeks** – Durations, expressed in weeks, between one date (*date1*) and another later date (*date2*) are calculated using the following formula: duration in weeks =  $(date2 - date1 + 1) / 7$ .
- **Months** – Durations, expressed in months, between one date (*date1*) and another later date (*date2*) are calculated using the following formula: duration in months =  $(date2 - date1 + 1) / 30.4375$ .

- **Years** – Durations, expressed in years, between one date (*date1*) and another later date (*date2*) are calculated using the following formula: duration in years =  $(\text{date2} - \text{date1} + 1) / 365.25$ .
- **Body Mass Index (BMI)** -  $\text{BMI (kg/m}^2\text{)} = \text{weight (kg)} / [\text{height (cm)} / 100]^2$
- **Estimated Glomerular Filtration Rate (eGFR)** -  
 $\text{eGFR (mL/min/1.73 m}^2\text{)} = 175 \times (\text{serum creatinine in mg/dL})^{-1.154} \times (\text{Age in years})^{-0.203} \times (0.742 \text{ if female}) \times (1.212 \text{ if African American})$ .

Note that age on consent date is collected on the CRF and will not be calculated.

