**Table 14.3.4.5.2**  
**Central ECG Data – Change from Baseline in Investigator’s Overall Interpretation of Clinical Significance by Visit**  
**Safety Population**

Target Visit	AD (N= ) Baseline 			bvFTD (N= ) Baseline 				All Subjects (N= ) Baseline 	
	Normal	Abnormal CS	Abnormal NCS	Normal	Abnormal CS	Abnormal NCS	Normal	Abnormal CS	Abnormal NCS
Week 26	(n=)	(n=)	(n=)	(n=)	(n=)	(n=)	(n=)	(n=)	(n=)
Normal	n (%)	n (%)	n (%)	n (%)	n (%)	n (%)	n (%)	n (%)	n (%)
Abnormal NCS	n (%)	n (%)	n (%)	n (%)	n (%)	n (%)	n (%)	n (%)	n (%)
Abnormal CS	n (%)	n (%)	n (%)	n (%)	n (%)	n (%)	n (%)	n (%)	n (%)
Week 52	(n=)	(n=)	(n=)	(n=)	(n=)	(n=)	(n=)	(n=)	(n=)
Normal	n (%)	n (%)	n (%)	n (%)	n (%)	n (%)	n (%)	n (%)	n (%)
Abnormal NCS	n (%)	n (%)	n (%)	n (%)	n (%)	n (%)	n (%)	n (%)	n (%)
Abnormal CS	n (%)	n (%)	n (%)	n (%)	n (%)	n (%)	n (%)	n (%)	n (%)
...									

Note: CS = Clinically Significant, NCS = Not Clinically Significant. The clinical significance was determined by the investigator.

Baseline is defined as the last non-missing value among triplicate values prior to first dose of study drug.

path\t\_program.sas date      time

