**Table 14.3.4.5.3**  
**Central ECG Data – QTc Abnormalities**  
**Safety Population**

ECG Parameter	Target Visit	AD (N= )	bvFTD (N= )	All Subjects (N= )
QTcF Interval (msec)	Baseline 	(n= )	(n= )	(n= )
	>450 ms to ≤480 ms	n (%)	n (%)	n (%)
	>480 ms to ≤500 ms	n (%)	n (%)	n (%)
	>500 ms	n (%)	n (%)	n (%)
	Week 26	(n= )	(n= )	(n= )
	>450 ms to ≤480 ms	n (%)	n (%)	n (%)
	>480 ms to ≤500 ms	n (%)	n (%)	n (%)
	>500 ms	n (%)	n (%)	n (%)
	Change from Baseline to Week 26	(n= )	(n= )	(n= )
	>30 ms to ≤60 ms	n (%)	n (%)	n (%)
	>60 ms to <90 ms	n (%)	n (%)	n (%)
	≥90 ms	n (%)	n (%)	n (%)
	...			
QTcB Interval (msec)				
...				

[figure not shown]
 Baseline is defined as the mean of the last non-missing triplicate values prior to first dose of study drug.  
Note: The categories are based on the average of triplicate measurements from central read (BIOCLINICA).

path\t\_program.sas date time

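### SAP 7.5 measures QTc change from the first 020 ECG, while the protocol and the SAP's own table shell use a pre-dose Baseline; for subjects dosed well before protocol version 3.0, the 7.5 reference is an on-treatment ECG

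*SAP*

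**What the plan says.** Three places govern this one output.

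- **SAP 7.5.** The change categories (>30 to ≤60, >60 to <90, ≥90 msec) are headed "Change from first 020 measurement". Nothing requires that measurement to precede dosing. The same section says: "A 12-lead ECG (triplicate recording) was introduced in protocol version 3.0". Local ECGs, optional before that version, are only listed.
- **Protocol 9.6.4.** "Subjects are also to be categorized and enumerated on the basis of QTc interval and change from Baseline as follows", with the same cut-points. It adds: "Tabular summaries and analyses are to be based on the central ECG data".
- **SAP Appendix G, Table 14.3.4.5.3.** The row is labelled as change from Baseline to Week 26, and the footnote reads: "Baseline is defined as the mean of the last non-missing triplicate values prior to first dose of study drug".

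The general rules agree with the protocol and the shell. SAP 4 states: "For purposes of calculations of change from baseline, Baseline (Visit 1) for the open-label study will be used". SAP 4.2 states: "A baseline value, unless specified otherwise, is the last non-missing value recorded prior to the first dose of study drug in 020". The proviso in 4.2 means that a specific rule such as the one in 7.5 can override it.

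**The concern.** One programmer could follow 7.5 and another the shell, and each would have a document in support. The choice matters for subjects whose first 020 central ECG came after dosing began. For them the 7.5 rule compares one on-treatment ECG with another, and the result would appear in a row labelled change from Baseline. A stable drug-related prolongation already present at the reference ECG would cancel. Long-term safety is a primary objective, and these categories are the plan's summary of individual QTc increases.

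**Working it through.** **Inputs**

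- Version 3.0 is dated 24 March 2016 (SAP 1; Protocol Appendix B).
- SAP 8.2 uses 020 data collected before the CRF migration of 24 August 2015, so some subjects had entered by then.
- ECGs are scheduled every 26 weeks (Protocol 4.4). Week 26 is day 183 ± 14, i.e. 169 to 197. Week 52 is day 365 ± 14, i.e. 351 to 379 (Protocol Figure 4-1). Week 78 is scheduled for day 546 (SAP Appendix A).
- Study day = date − first dose + 1 (SAP 4.2).

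**Which ECG becomes the 7.5 reference**

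1. From 24 August 2015 to 24 March 2016 is 213 days. A subject dosed by the earlier date was at study day 213 + 1 = 214 or later, beyond day 197. The Week 26 ECG visit had passed.
2. The same holds for any first dose on or before 9 September 2015: 197 days elapsed gives study day 198, which is past 197. The first scheduled central ECG in 020 is then Week 52, day 351 at the earliest.
3. For a first dose on or before 11 March 2015, 379 days had elapsed, giving study day 380, which is past 379. The Week 52 window had also closed, so the first scheduled ECG is Week 78 or later.
4. An early-termination or unscheduled ECG could come sooner, but would still follow the first dose. Sites adopting version 3.0 after its date would push the reference later.

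**Effect on the categories**

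The plan gives no figure to reproduce, and the study has no sample-size calculation. The number affected, any QTc shift and the SD of change are not in the documents. The inputs below are assumptions, used only to show direction and range.

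Take change as normal with SD s and a stable on-drug shift d. Against a pre-dose reference, P(change > 30) = P(Z > (30 − d)/s). Against an on-treatment reference the shift cancels, so P(0) = P(Z > 30/s), taking the same s. If a share f of the subjects measured at a visit is affected, the 7.5 text gives f·P(0) + (1 − f)·P(d). This applies only at visits after the reference visit.

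With s = 15 msec:

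| d (msec) | Pre-dose reference | 7.5 text, f = 10% | 7.5 text, f = 50% |
|---|---|---|---|
| 0 | 2.3% | 2.3% | 2.3% |
| 5 | 4.8% | 4.5% | 3.5% |
| 10 | 9.1% | 8.4% | 5.7% |
| 20 | 25.2% | 23.0% | 13.8% |

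For d = 10 and f = 50%, moving s from 12 to 18 msec gives 4.8% to 13.3% against a pre-dose reference and 2.7% to 9.1% under the 7.5 text.

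At the reference visit itself an affected subject's change is exactly zero. For d = 10, s = 15, f = 50%, the figure there is 0.5 × 9.12% = 4.6%, not 5.7%. Before that visit the affected subjects have no scheduled 020 ECG and contribute nothing.

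**The case against.** The strongest reply is that 7.5 is deliberate. SAP 7.2 and 7.3 say that baseline data may come from the prior study if not repeated in 020. SAP 7.5 omits that sentence, notes the late arrival of triplicate ECGs and names its own reference, which the proviso in 4.2 permits. Protocol 9 and SAP 9 send changes to the study report. On this reading the text keeps subjects who have no pre-dose ECG, and only the shell is wrong. That may be so, but the row label and footnote would then misdescribe those subjects' data, so a correction is needed either way.

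The impact is also limited, and this stands. The study is descriptive. The rows at issue are one block of one table, and nothing is lost if the programmer follows the shell. Absolute QTc categories, mean change in Table 14.3.4.5.1, the individual listings and the >500 msec criterion do not depend on the 7.5 reference.

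Two wider readings are tempting but not supported:

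- A reader might infer that subjects whose prior-study ECG fell within 42 days, and so was not repeated, are affected too. Under Protocol Table 4-1, footnote a, that ECG serves as Baseline (Day 1). If it counts as the first 020 measurement, the two references coincide.
- A reader might take footnote 1 of SAP 4.1, which lists mapped data without ECGs, as proof that prior-study ECGs will not be imported. Laboratory and vital-sign data are missing from that list as well, yet 7.2 and 7.3 use prior-study baselines for them.

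**Conclusion.** The contradiction is established from the text. So is the direction of its effect if 7.5 is programmed: an affected subject's stable prolongation is understated in the change categories, and there is no distortion if there is no shift. Increases arising after the first 020 ECG are still captured.

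The size is not established. A reader might infer from the table above that a known fraction of QTc outliers would be missed. The documents do not support that, since the affected share, the shift and the SD are all assumed. Nor is Week 52, or about one year on drug, the reference for every early entrant. It is a lower bound for scheduled ECGs.

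The conclusion assumes that subjects with data before 24 August 2015 were dosed at Visit 1, remained on study, and had no earlier unscheduled or early-termination central ECG. It also assumes that a prior-study ECG is not counted as the first 020 measurement. Whether a centrally read ECG exists from the end of the originating studies is not stated. Severity is minor to should-fix.

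**What to change.** 1. In SAP 7.5 replace "Change from first 020 measurement" with: *Change from Baseline (last non-missing centrally read ECG, mean of available readings, on or before the date of first 020 dose; this may come from the prior study if not repeated in 020, as in 7.2 and 7.3)*.
2. Align the Baseline footnote of Table 14.3.4.5.3. Listing 16.2.9.8.1 already allows an average of the available readings.
3. Report the number of subjects with no pre-dose central ECG, and keep them in the absolute QTc categories.
4. If change is shown for them, put change from first on-treatment ECG in a separate, labelled row.

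The cost is one phrase, one footnote, one count and possibly an import of prior-study ECGs. The change-from-Baseline rows may hold fewer subjects: in the illustrative case with half of 1000 subjects affected and none having a pre-dose central ECG, 500 would remain. The separate row keeps the others visible without calling their reference Baseline.
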